--	--	--

**Complete as required, all abbreviations used in the protocol should be defined upon first mention and added to this table**

ACR	American College of Rheumatology
AE	Adverse Event
BOLD	Blood oxygenation level dependent
CDAI	Clinical Disease Activity Index
CI	Chief Investigator
CNORIS	Clinical Negligence and Other Risks Indemnity Scheme
CNS	Central Nervous System
DAN	Dorsal Attention Network
DAS	Disease Activity Score
DMARD	Disease-Modifying Anti-Rheumatic Drug
DMN	Default Mode Network
DOI	Digital Object Identifier
eCRF	Electronic case report form
EL	Engagement Leads
EPR	Electronic Patient Record
EPSI	Echo-planar Spectroscopic Imaging
EULAR	European League Against Rheumatism
fMRI	Functional Magnetic resonance imaging
GAIN	Glasgow Arthritis Involvement Network
GluCEST	Glutamate Chemical Exchange Saturation Transfer
ICA	Independent Component Analysis
IMID	Immune-mediated inflammatory diseases
JAK	Janus Kinase
JAKi	Janus Kinase Inhibitor
LIPL	Left Inferior Parietal Lobule
MRS	Magnetic Resonance Spectroscopy
NMDA	N-methyl-d-aspartate
PPI	Patient and Public Involvement
PPT	Pressure Pain Thresholds

**SOAR - Exploiting Leading Edge 7T MRI Brain Imaging to Decipher Olumiant's Mode of Analgesic Action in Rheumatoid Arthritis**

GLASGOW CLINICAL TRIALS UNIT

FORM 51.001A

V7.0

PROMIS	Patient Reported Measurement Information Service
PRP	Patient Research Partner
QST	Quantitative Sensory Testing
RA	Rheumatoid Arthritis
RACE	Research into Inflammatory Arthritis Centre Versus Arthritis
REC	Research Ethics Committee
ROI	Region of Interest
SAE	Serious Adverse Event
SBA	Seed-Based Correlation Analysis
SDAI	Simple Disease Activity Index
STAT	Signal Transducer and Activator of Transcription
7T	7 Tesla
TMG	Trial Management Group
TNF	Tumour Necrosis Factor

## **STUDY SYNOPSIS**

Title of Study	Exploiting Leading Edge 7T MRI Brain Imaging to Decipher Olumiant's Mode of Analgesic Action in Rheumatoid Arthritis
Lead Study Centre	University of Glasgow/NHS Greater Glasgow and Clyde
Duration of Study	24 months
Primary Objective	
1) To evaluate the effects of Olumiant on Default Mode Network (DMN)-Insula connectivity and insular glutamate levels in rheumatoid arthritis (RA) (neurobiological markers of fibromyalgia).
 
2) To evaluate the effects of Olumiant on Dorsal Attention Network (DAN)-Left Inferior Parietal Lobule (LIPL) connectivity in RA (neurobiological marker of peripheral inflammation).

Secondary Objective	To explore the relationship between pain, clinical phenotype, peripheral immune markers and their change with MRI markers indicative of CNS pathway function.
Primary Endpoints	The primary neuroimaging metrics of interest are functional connectivity and glutamate concentration
Rationale	
The revolution in rheumatoid arthritis therapeutics has been transformative for many patient outcomes. Yet most patients continue to experience life disabling pain. Strikingly, even those who achieve full disease remission with state-of-the-art anti-tumour necrosis factor (TNF) treatments report substantially higher levels of pain when compared to the general population. Such disconnect presents one of the greatest contemporary challenges to the care of patients with RA.
 
Considering the ongoing excess burden of pain in this patient population, RA patients receiving Olumiant, a Janus Kinase (JAK) 1/2 inhibitor, report superior and more rapid pain improvements in comparison to those receiving anti-TNF therapy. However, the majority of this effect could not be explained by markers of peripheral inflammation and remains to be understood.

Methodology	This single-centre, single arm observational cohort study will allow us to investigate Olumiant's mechanism of analgesic action in RA patients.
Sample Size	20 participants
Screening	Patients with active RA attending clinics in NHS Greater Glasgow and Clyde who are scheduled to begin Olumiant as part of their standard NHS clinical care will be asked to contribute to this study by their point of care team.
Inclusion Criteria	
 
• Adults <math>\geq</math> 18 years <math><</math> 75 years.
 
• Clinical diagnosis of RA
 
• Selected to start Olumiant by their usual rheumatology clinical team in line with local guidance (previous failure of at least 2 DMARDs and moderate to severe active disease).
 
• Right-handed (to reduce neuroimaging heterogeneity).
 

Exclusion Criteria	
 
• Inability to provide written informed consent.
 

**SOAR - Exploiting Leading Edge 7T MRI Brain Imaging to Decipher Olumiant's Mode of Analgesic Action in Rheumatoid Arthritis**

GLASGOW CLINICAL TRIALS UNIT

FORM 51.001A

V7.0

	
 
• Severe physical impairment (e.g. blindness, deafness, paraplegia).
 
• Pregnant or breast feeding.
 
• Contraindications to MRI (e.g. severe claustrophobia).
 
• Major confounding neurological disease including Multiple Sclerosis, Stroke, Traumatic Brain Injury, Parkinson's Disease, Alzheimer's Disease
 
• Previous targeted synthetic (e.g. Olumiant, tofacitinib) DMARD exposure.
 
• Co-morbid medical conditions that may significantly impair physical functional status
 
• Medical or psychiatric conditions that in the judgment of study personnel would preclude participation in this study (e.g., malignancy, psychosis, suicidal ideation)
 
• BMI > 40 or unable to lie comfortably in MRI
 

Product, Dose, Modes of Administration	Olumiant will be administered following standard of care guidelines.
Duration of Study Participation	12 weeks
Statistical Analysis	To assess whether treatment with Olumiant results in a reduction in functional connectivity (DMN-Insula and DAN-IPL) and glutamate quantification, changes in our neuroimaging metrics of interest between time points will be evaluated using paired t-tests. Changes in pain, clinical phenotyping and immunophenotyping measures will be correlated with those significant regions identified from our primary objective. Putative confounders will be explored using general linear models.

**Participant identification**

- Identification by direct care team
- Provision of PIS

**Phone call**

Research team gauge interest and assess eligibility

**Visit 1: Screening & Baseline (Day 0)**

- Informed consent
- Review of inclusion/exclusion criteria
- Demographics
- Medical history
- Clinical assessment
- Sickness behaviour questionnaires
- Bloods for immunophenotyping
- 7T MR sequences
- Optional joint ultrasound
- Optional quantitative sensory testing

**Visit 2 (Week 12 ± 14 days)**

- Clinical assessment
- Sickness behaviour questionnaires
- Bloods for immunophenotyping
- 7T MR sequences
- Optional joint ultrasound
- Optional quantitative sensory testing

Olumiant treatment

**SOAR - Exploiting Leading Edge 7T MRI Brain Imaging to Decipher Olumiant's Mode of Analgesic Action in Rheumatoid Arthritis**

GLASGOW CLINICAL TRIALS UNIT

FORM 51.001A

V7.0

Study Procedure	Visit 1 - Screening & Baseline	Visit 2 - 12 week
Inclusion/exclusion criteria	✓	
Informed consent	✓	
EULAR Disease Activity Score (DAS28)	✓	✓
ACR/EULAR Classification Criteria for RA	✓	
CDAI	✓	✓
SDAI	✓	✓
7-Day Symptom Diary (Numeric Rating Scale)	✓	✓
American College of Rheumatology Fibromyalgia Scale	✓	✓
McGill Pain Questionnaire	✓	✓
Michigan Body Map Regional Pain	✓	✓
PROMIS-Depression	✓	✓
PROMIS-Anxiety	✓	✓
PROMIS-Fatigue	✓	✓
PROMIS-Sleep related impairment	✓	✓
PROMIS-Physical functioning short form	✓	✓
PROMIS-Pain inference	✓	✓
Pain NRS Pain Number Rating Scale	✓	✓
FACIT-Fatigue Scale	✓	✓
Global Impression Of Change (participant)		✓
Cognitive Failures Questionnaire	✓	✓
Sickness Questionnaire	✓	✓

**SOAR - Exploiting Leading Edge 7T MRI Brain Imaging to Decipher Olumiant's Mode of Analgesic Action in Rheumatoid Arthritis**

GLASGOW CLINICAL TRIALS UNIT

FORM 51.001A

V7.0

Demographics	✓	
BMI	✓	
Drug Assessment	✓	✓
Past Medical History	✓	
Blood sample for immunophenotyping*	✓	✓
7T magnetic resonance protocol	✓	✓
Ultrasound of joints**	✓	✓
Quantitative sensory testing (QST)**	✓	✓
Recording of Adverse Events		✓

\* Blood sample schedule outlined in 4.4 LABORATORY TESTS

\*\* Consent to these procedures is optional

## 1 INTRODUCTION

### 1.1 RATIONALE

The revolution in rheumatoid arthritis (RA) therapeutics has been transformative for many patient outcomes. Yet most patients continue to experience life disabling pain. Strikingly, even those who achieve full disease remission with state-of-the-art anti-TNF treatments report substantially higher levels of pain when compared to the general population. Such disconnect presents one of the greatest contemporary challenges to the care of patients with RA.

Considering the ongoing excess burden of pain in this patient population, the RA-BEAM trial presented welcome data. RA patients randomised to Olumiant, a JAK1/2 inhibitor, reported superior and more rapid pain improvements in comparison to those receiving anti-TNF therapy. However, the majority of this effect could not be explained by markers of peripheral inflammation and remains to be understood.

### 1.2 BACKGROUND

We believe that RA is a mixed pain state i.e. pain pathways exist in addition to established peripheral inflammatory nociceptive mechanisms. In particular, the central nervous system (CNS) may have an important role in determining RA pain. Recently our group were the first to delineate distinct neurobiological pain signatures in the brains of RA patients by employing 3T functional connectivity magnetic resonance imaging (fcMRI) – a recent adaptation of functional MRI data that examines the synchrony of neural activity which modulates the efficiency and extent of neuronal transmission between brain regions. Specifically, we identified and replicated two distinct pain signatures: a) enhanced functional connectivity between the Default Mode Network (DMN) and insula which was unrelated to levels of peripheral inflammation but, intriguingly, is an established neurobiological marker of fibromyalgia (an archetypal CNS determined chronic pain disorder) and b) enhanced functional connectivity between the Dorsal Attention Network (DAN) and the left inferior parietal lobule (LIPL) which was related to levels of peripheral inflammation.

Pre-clinical experiments have not only implicated the JAK- signal transducer and activator of transcription (STAT) pathway with peripheral immune system functioning but also the brain. In the CNS, this pathway promotes gene expression associated with inflammation which in turn generates pro-nociceptive cytokines such as TNF $\alpha$ . However, there is now also emerging evidence to support the pathway's direct role in synaptic transmission and neurotransmitter receptor modulation. Specifically, the JAK-STAT pathway appears important in N-methyl-d-aspartate (NMDA) related synaptic plasticity – a ubiquitous glutamate receptor of the human brain. Their induction is selectively blocked by JAK inhibitors and JAK2 knockdown abolishes NMDA functioning. Increases in glutamate and subsequent binding to NMDA receptors cause chaotic and incoherent neuronal functional activity. In human studies of fibromyalgia, we have consistently evidenced both elevated glutamate levels within the insula and dysfunctional neural connectivity. Moreover, we have shown that fibromyalgia pharmacotherapy (pregabalin), considered to reduce neural glutamate, rectifies both insular glutamate and pro-nociceptive brain functional connectivity (DMN-insula). JAK inhibition (JAKi) may facilitate the reduction of glutamate-NMDA binding and ultimately pain alleviation by normalising the functional activity of these same neural connections.

There are clear practical constraints of sampling fresh human brain tissue in order to interrogate these possible mechanisms. Instead, neurobiological surrogate imaging measures may be employed. In Glasgow we benefit from the only clinical based ultra-high resolution 7T MRI scanner in the UK. Unlike lesser resolutions, 7T can distinguish the resonance of glutamate from other metabolites and so more precisely quantify our chemical of interest. Further, the superior spatial resolution of 7T enhances capacity to indirectly measure neuronal functional connectivity.

### **1.3 STUDY HYPOTHESIS**

We hypothesise that Olumiant's mechanism of analgesic action is determined by at least two factors. The first is related to those pathways seen in fibromyalgia, mediated via DMN-insula connectivity and insular glutamate. The second is related to peripheral inflammation, mediated via DAN-LIPL.

## **2 STUDY OBJECTIVES**

- 1) To evaluate the effects of Olumiant on DMN-Insula connectivity and insular glutamate levels in RA (neurobiological markers of fibromyalgia).
- 2) To evaluate the effects of Olumiant on DAN-LIPL connectivity in RA (neurobiological marker of peripheral inflammation).
- 3) To explore the relationship between pain, clinical phenotype, peripheral immune markers and their change with MRI markers indicative of CNS pathway function.

### **2.1 PRIMARY ENDPOINT**

The primary endpoints are changes in:

- brain functional connectivity (DMN-Insula and DAN-LIPL) as measured by 7T MRI
- insular glutamate signal as measured by 7T MRS

Between baseline and visit 2 (week 12)

### **2.2 SECONDARY ENDPOINT(S)**

- Changes in clinical phenotype, pain, depression and anxiety as measured by:
  - EULAR Disease Activity Score (DAS28)
  - CDAI
  - SDAI
  - 7-Day Symptom Diary (Numeric Rating Scale)
  - American College of Rheumatology Fibromyalgia Scale
  - McGill Pain Questionnaire
  - PROMIS-Depression
  - PROMIS-Anxiety
  - PROMIS-Fatigue
  - PROMIS-Sleep related impairment
  - PROMIS-Physical functioning short form
  - PROMIS-Pain inference
  - Pain Number Rating Scale
  - FACIT-Fatigue Scale
  - Global Impression of Change (participant)
  - Cognitive Failures Questionnaire
  - Sickness Questionnaire
  - Synovitis score (from joint ultrasound)
  - Pain sensitivity variables (from QST measures)
- Changes in inflammatory cytokines/chemokines Between baseline and visit 2 (week 12)

## **3 STUDY DESIGN**

This study will be performed according to the UK policy framework for health and social care research (version 3.3, 07 November 2017).

The trial design is detailed below and is summarised in STUDY FLOW CHART and SCHEDULE OF ASSESSMENTS. The trial is a single-centre observational cohort study to test the hypothesis that Olumiant's mechanism of analgesic action is determined by at least two factors, the first relating to pathways seen in fibromyalgia, and the second relating to peripheral inflammation.

### **3.1 STUDY POPULATION**

The study will involve participants aged over 18 years with RA who are scheduled to start outpatient Olumiant as part of standard clinical practice, who meet the inclusion criteria below and who have none of the specified exclusion criteria. All will give full informed consent.

### **3.2 INCLUSION CRITERIA**

- Adults  $\geq$  18 years  $<$  75 years.
- Clinical diagnosis of RA
- Selected to start Olumiant by their usual rheumatology clinical team in line with local guidance (previous failure of at least 2 DMARDs and moderate to severe disease active disease)
- Right-handed (to reduce neuroimaging heterogeneity)

### **3.3 EXCLUSION CRITERIA**

- Inability to provide written informed consent.
- Severe physical impairment (e.g. blindness, deafness, paraplegia).
- Pregnant or breast feeding.
- Contraindications to MRI (e.g. severe claustrophobia).
- Major confounding neurological disease including Multiple Sclerosis, Stroke, Traumatic Brain Injury, Parkinson's Disease, Alzheimer's Disease
- Previous targeted synthetic (e.g. Olumiant, tofacitinib) DMARD exposure.
- Co-morbid medical conditions that may significantly impair physical functional status
- Medical or psychiatric conditions that in the judgment of study personnel would preclude participation in this study (e.g., malignancy, psychosis, suicidal ideation)
- BMI  $>$  40 or unable to lie comfortably in MRI

### **3.4 IDENTIFICATION OF PARTICIPANTS AND CONSENT**

Patients with active RA attending clinics in NHS Greater Glasgow and Clyde who are scheduled to begin Olumiant as part of their standard NHS clinical care will be asked to contribute to this study by their point of care team. The direct care team will notify patients of the study, provide a participant information sheet and seek their consent for the research team to contact them by telephone. at least 24 hours later to gauge their interest in the study and allow them to ask any questions. Eligibility will be confirmed by a medically qualified investigator. A record will be kept on the CRF detailing if the telephone call was made, if contact was indeed established and the outcome of the telephone call.

If the patient is interested and eligible, they will be invited to attend Visit 1 where they will first undertake informed consent. At this meeting, subjects will be asked again if they have any questions and those who wish to participate will be asked to sign the consent form. Two copies will be signed (one each for the participant and the site file) and a copy of the signed consent form will be inserted into the patient's record or scanned into the electronic patient record (EPR). A letter will be sent to the patient's GP to inform them of their participation in the study.

Consent will be taken by a member of the research team.

Reasonable travel expenses will be reimbursed.

### **3.5 WITHDRAWAL OF SUBJECTS**

Participants can decide to withdraw from the study at any time without providing a reason. The participant needs to request this formally and a withdrawal document will be completed and signed by the research staff. They have the option to either withdraw from the study completely or from parts of it.

Participants will have the option to remain in the study irrespective of stopping treatment. The Chief Investigator (CI) or co-investigators also have the right to withdraw patients from the study if deemed in the best interests of the patient or in the event of Adverse Events (AEs), protocol violations, loss of capacity for continuous consent, administrative or other reasons. Full details of withdrawal will be recorded on the electronic Case Report Form (eCRF).

Participants may decide to withdraw their initial consent for this study, at this point no further information regarding the participant will be collected. Data relating to the patient that has been collected up to the point of withdrawal will still be used unless the participant specifies they do not wish this to happen. Any stored blood samples that can still be identified as the participants will be destroyed if the participants wish this.

## 4 TRIAL PROCEDURES

### 4.1 STUDY SCHEDULE

The study will comprise of a total of 2 research visits.

#### 4.1.1 Screening & Baseline (Day 0)

- Informed consent
- Review of inclusion / exclusion criteria
- ACR/EULAR Classification Criteria for RA
- EULAR Disease Activity Score (DAS28)
- CDAI
- SDAI
- 7-Day Symptom Diary (Number Rating Scale)
- American College of Rheumatology Fibromyalgia Scale
- McGill Pain Questionnaire
- Michigan Body Map Regional Pain
- PROMIS-Depression
- PROMIS-Anxiety
- PROMIS-Fatigue
- PROMIS-Sleep related impairment
- PROMIS-Physical functioning short form
- PROMIS-Pain inference
- Pain Number Rating Scale
- FACIT Fatigue Scale
- Cognitive Failures Questionnaire
- Sickness Questionnaire
- 7T MRI protocol
- Ultrasound of joints of interest
- Quantitative sensory testing (QST)
- Blood draw for immunophenotyping
- Demographics
- BMI
- Drug Assessment
- Past Medical History

Estimated visit time 4 hours

#### 4.1.2 VISIT 2 : Week 12 ± 14 days

- ACR/EULAR Classification Criteria for RA
- EULAR Disease Activity Score (DAS28)
- CDAI
- SDAI
- 7-Day Symptom Diary (Number Rating Scale)
- American College of Rheumatology Fibromyalgia scale

- McGill Pain Questionnaire
- Michigan Body Map Regional Pain
- PROMIS-Depression
- PROMIS-Anxiety
- PROMIS-Fatigue
- PROMIS-Sleep related impairment
- PROMIS-Physical functioning short form
- PROMIS-Pain inference
- Pain Number Rating Scale
- FACIT Fatigue Scale Global Impression of Change (participant)
- Cognitive failures questionnaire
- Sickness Questionnaire
- 7T MRI protocol
- Ultrasound of joints of interest
- Quantitative sensory testing (QST)
- Blood draw for immunophenotyping
- Drug assessment

Estimated visit time 3.5 hours

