## **4.3 STUDY OUTCOME MEASURES**

### **4.3.1 Primary Outcome Measure(s)**

The primary outcome measures will be:

1. brain functional connectivity (DMN-Insula and DAN-LIPL) as measured by 7T MRI
2. insular glutamate signal as measured by 7T MRS

Between baseline and visit 2 (week 12) following Olumiant treatment in RA.

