### **5 Study Medication**

#### **5.1 OLUMIANT TREATMENT SCHEDULE & ADMINISTRATION**

Olumiant (4mg) will be administered in line with standard of care guidance. This is the standard dose in line with license for use in active moderate to severe RA. A dose adjustment from 4mg to 2mg is permitted during the study depending on side-effects.

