### **5.3.1 Supply of Study Treatment**

The study site will be responsible for procurement of all Olumiant via usual NHS supply mechanisms for medicines.

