### 7.2 PRIMARY EFFICACY ANALYSIS

The primary outcomes are changes in brain functional connectivity (DMN-Insula and DAN-LIPL) and changes in insular glutamate signal from baseline (day 0) to Visit 2 (week 12), following Olumiant treatment in RA.

Resting state fMRI data will be pre-processed to control transient head movements and parcellated into cortical areas and subcortical nuclei before estimation of a functional connectivity matrix for each subject under each treatment condition. Topological analysis of weighted graphs derived from these matrices will estimate brain network properties such as weighted nodal degree and modular community structure,

which are known to be sensitive to the effects of peripheral CRP and are hypothetically expected to be indicative also of the effects of Olumiant treatment on functional brain networks.

Objective 1 and 2: To assess whether treatment with Olumiant results in a reduction in functional connectivity (DMN-Insula and DAN-IPL) and glutamate levels, changes in our neuroimaging metrics of interest between time points will be evaluated using paired t-tests.

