### **9.2 RECORD RETENTION**

To enable evaluations and/or audit from regulatory authorities, the investigator agrees to keep records, including the identity of all participating subjects (sufficient information to link record), all original signed informed consent forms, serious adverse event forms, source documents, and detailed records of treatment disposition in accordance with ICH GCP, local regulations, whichever is longer. In line with the University of Glasgow's Code of Good Research Practice study data will be retained for a minimum of 10 years.

Archive coded information will be retained for a maximum of 10 years after the end of this trial and for its transmission outside the European Economic Area.

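### Should the Visit 2 window be counted from the first Olumiant dose instead of from the baseline visit?

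*Combined protocol and SAP*

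**What the plan says.** The heading of section 4.1.1 begins "Screening & Baseline (Day 0", so consent, screening and the baseline scan share one visit, which is the time origin. Section 4.1.2 is headed "VISIT 2 : Week 12 ± 14 days", and the flow chart gives the same window. Neither names the event from which the weeks are counted.

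The primary outcomes are tied both to that origin and to treatment. Section 7.2 speaks of "changes in insular glutamate signal from baseline (day 0) to Visit 2 (week 12), following Olumiant treatment in RA", and section 4.3.1 of change "Between baseline and visit 2 (week 12) following Olumiant treatment in RA". The synopsis gives 12 weeks as the duration of participation.

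Treatment itself belongs to routine care. Section 3.1 recruits patients "who are scheduled to start outpatient Olumiant as part of standard clinical practice", and section 5.3.1 says "The study site will be responsible for procurement of all Olumiant via usual NHS supply mechanisms for medicines". The visit lists show a drug assessment at both visits, and section 9.2 requires the keeping of "detailed records of treatment disposition". Section 3.3 excludes earlier exposure to Olumiant, so the first dose comes after the eligibility check. Sections 7.1 and 7.3 plan general linear models for possible confounders, and section 7.1 promises a separate statistical analysis plan, which is not in the text supplied.

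**The concern.** The study is single-arm and compares each participant with their own baseline by a paired t-test, with about 17 evaluable participants (section 7.6). There is no control arm to absorb differences in treatment time, so a shortened or uneven time on drug goes straight into the paired differences.

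The protocol has two clocks. The visit clock starts at the research visit; the treatment clock starts when routine care delivers the first dose. The Visit 1 procedure lists contain no dispensing or first dose, and nothing readable caps the interval between the two. Two coordinators could book Visit 2 from different dates and both comply with section 4.1.2. A delay after baseline would shorten treatment at the second scan, possibly to well under 12 weeks, and could weaken the imaging change that the study is meant to detect. The natural remedy would seem to be to count the window from the first dose.

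**Working it through.** **1. The plan's own window.** 12 × 7 = 84 days; 84 ± 14 gives days 70 to 98 after Visit 1.

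**2. Same gap for everyone.** Let g be the days from Visit 1 to first dose. Time from first dose to the second scan is (70 to 98) − g. The documents do not give g, so these values are assumptions:

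| g (days) | First dose to Visit 2 (days) |
|---|---|
| 0 | 70 to 98 |
| 7 | 63 to 91 |
| 14 | 56 to 84 |
| 21 | 49 to 77 |

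**3. Gap varying between participants.** Assume that visits are spread evenly over days 70 to 98 and that gaps are spread evenly over 0 to G days, independently. Then the mean is 84 − G/2, the SD is √(28²/12 + G²/12), and the share under 70 days is G/56:

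| G (days) | Mean | SD | Under 70 days |
|---|---|---|---|
| 0 | 84 | 8.1 | 0% |
| 7 | 80.5 | 8.3 | 12.5% |
| 14 | 77.0 | 9.0 | 25% |
| 21 | 73.5 | 10.1 | 37.5% |

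The G = 0 row is also what counting from first dose would give. The permitted ± 14 days accounts for most of the spread in every row. The 70-day mark is only a yardstick, since the protocol sets no minimum time since first dose.

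**4. Power.** Section 7.6 states no power, effect size or SD, so a loss cannot be derived from the documents. For scale only, assume 80% power at n = 17, two-sided 0.05 (standardised paired effect 0.724) and Visit 2 on day 84. The answer depends on the assumed time course and on how the gap is spread:

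| Assumption | 7 days | 14 days | 21 days |
|---|---|---|---|
| Common gap, effect proportional to (84 − g)/84 | 73% | 65% | 56% |
| Common gap, square of that fraction | 65% | 50% | 35% |
| Gap spread evenly from 0 to the stated value, linear effect | 77% | 73% | 69% |
| Common gap, effect levelling off (time constant 28 days) | 79% | 77% | 75% |

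For the third row the mean fraction is 1 − G/168 = 0.958, 0.917, 0.875. For the last, the fraction is (1 − e^(−(84 − g)/28))/(1 − e^(−3)) = 0.985, 0.966, 0.941. With no gap, or with an effect complete by the shortest treatment time, nothing is lost. The documents give no imaging time course with which to choose between the rows.

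**5. What counting from first dose would do.** Time from first dose becomes 70 to 98 days whatever the gap. The scan-to-scan interval becomes (70 to 98) + g days, so the variation moves from treatment time to the interval between the paired measurements. Section 5.2.1 also restricts triamcinolone for 8 weeks (56 days) around the baseline and 12-week assessments. If that applies on both sides of each visit, the two periods cover 56 + 56 = 112 days between scans, which contains the present maximum of 98. With the new clock, 98 + g exceeds 112 once g is above 14, and part of the interval could then fall outside both periods.

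**The case for a change.** The strongest argument for a change is that the only stated time origin is a research visit, while the quantity of interest is change after treatment. Eligibility and consent are completed at Visit 1 and the drug comes through a separate routine pathway, so a gap is plausible. Recording the first-dose date and rewording the window would cost little, and a sensitivity model would use only one degree of freedom (16 to 15, critical t from 2.120 to 2.131).

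Part of this stands. The anchor is not written down in the readable text, and the bar on earlier exposure gives the order of events but not the interval. The drug assessment and the treatment records may hold the start date, yet no passage names it as a data field.

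What does not stand is the step from an unstated anchor to a faulty comparison. A plausible gap is not a demonstrated one, and the flow chart, whose layout is lost, or the separate analysis plan may settle it. Re-anchoring also leaves other variation in treatment in place: the ± 14 days remains, section 5.1 says "A dose adjustment from 4mg to 2mg is permitted during the study depending on side-effects", and section 3.5 lets participants stay in the study after stopping treatment.

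**Conclusion.** No change to the plan is needed. The readable text leaves the interval between baseline and first dose unstated, but its Day 0 label, 12 weeks of participation and outcome definitions fit a start at or close to Visit 1. On that reading the second scan falls 70 to 98 days into treatment, as intended, and the pre-post comparison is sound. If gaps do occur, each day takes one day off treatment time. The added spread is modest (SD 8.1 to 9.0 days for gaps of 0 to 14 days, under the even-spread assumptions), and the effect on power cannot be derived.

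A study team would ordinarily settle the anchor in its working documents, take the start date from the drug assessment or treatment records, and report time from first dose to Visit 2. If that time proved uneven, the general linear models already planned could include it. Re-anchoring the window with no limit on the gap is not clearly better: it trades steadier treatment time for a longer and more variable interval between scans.

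This conclusion rests on the gap being short. Records showing that first doses commonly came weeks after the baseline scan would reopen the point.
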